7. STUDY ASSESSMENTS AND EVALUATIONS

7.1 Overview

All patients should visit the study center on the days specified within this protocol. The complete Schedule of Assessments for this study is shown in Appendix D. The baseline physical examination, medical history, ECOG PS, 12-lead electrocardiogram (ECG), complete blood counts (CBC), differential and platelets, complete metabolic profile (CMP), prothrombin/partial thromboplastin time/international normalization ratio (PT/PTT/INR), and serum pregnancy test should be done \leq 7 days prior to initiation of treatment. If urine pregnancy test is being done, it must be performed within 72 hours of Cycle 1 Day 1. However, if these initial examinations are obtained within 72 hours of Cycle 1 Day 1 they do not have to be repeated on Cycle 1 Day 1. CT scans and LVEF assessment should be performed \leq 28 days prior to initiation of treatment, as should tumor markers, if appropriate.

7.2 Baseline Study Assessments

The following information will be collected and procedures will be performed for each patient at screening:

• Written informed consent prior to any other study-related procedures

CONFIDENTIAL

STUDY DRUG(S): CARFILZOMIB AMENDMENT 2 DATE: 25 FEBRUARY 2015

- Medical history (including clinical tumor assessment as appropriate)
- Physical examination, measurements of height (first visit), weight,
- Vital signs (resting heart rate, blood pressure [BP], respiratory rate, and oral temperature)
- ECOG performance status (see Appendix A)
- 12-lead electrocardiogram (ECG)
- Echocardiogram (ECHO) with calculated left ventricular ejection fraction (LVEF) (repeat if/when clinically indicated). Multigated acquisition (MUGA) scan is acceptable if ECHO is not available.
- Concomitant medication review
- CBC including hemoglobin, hematocrit, WBC with 3-part differential and platelets
- CMP to include: glucose, blood urea nitrogen (BUN), creatinine, sodium, potassium, chloride, calcium, carbon dioxide (CO₂), ALT, AST, alkaline phosphatase (ALP), total bilirubin, total protein, and albumin.
- PT/PTT/INR
- Fasting serum chromogranin A (overnight fasting required)
- Serum (within 7 days) or urine (within 72 hours) pregnancy test must be done before Cycle 1 Day 1
- CT scans of the chest, abdomen and pelvis ≤28 days prior to initiation of study treatment; CT scan of abdomen and pelvis is preferred, but CT scan of abdomen is acceptable.
- Archival tumor tissue or 10 unstained slides will be obtained if available

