1. INTRODUCTION

1.1 Background

Neuroendocrine malignancies refer to a diverse group of diseases that are generally rare however, their incidences are rapidly increasing. Among these, pancreatic neuroendocrine tumors (PNETs, islet cell tumor, islet cell carcinoma, or pancreatic carcinoid) account for up to 5% of all pancreatic malignancies. Functional PNET tumors make extra amounts of hormones (e.g. gastrin, insulin, and glucagon) and cause symptoms. Non-functional PNETs do not make extra amounts of hormones, and the symptoms are caused by the tumors as they grow. The majority of the non-functional tumors are malignant.

Gastrointestinal (GI) carcinoids are well-differentiated endocrine neoplasms that consist of a diverse group of tumors arising from cells of the diffuse endocrine system within the GI tract. These tumors are generally slow-growing and can be present throughout the GI tract. All GI carcinoids share common pathologic features that characterize them as well-differentiated neuroendocrine tumors (NETs) (Levy and Sobin. 2007). The World Health Organization (WHO) classification of GI NETs is clinically and prognostically useful for newly diagnosed patients with GI NETs because it accounts for specific biological behavior according to location and tumor differentiation. The specific biological behavior of a particular tumor type varies according to the cell of origin (Capella et al. 1995; Solcia et al. 2000).

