7.4 Response Assessment Every 3 Cycles

Patients will be evaluated for response to treatment after every 3 cycles of treatment. The following assessments will be performed:

- CT scans of chest, abdomen and pelvis (if abnormal at baseline)
- 24 hour urine for 5-HIAA

Patients with progressive disease or unacceptable toxicity should be discontinued from the study; patients with stable disease or response to therapy will continue treatment.

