7.6 Follow-up

7.6.1 Follow-up for Patients Who Discontinue Prior to Disease Progression

Patients who discontinue study treatment prior to the occurrence of disease progression will be followed every 3 months (± 1 month) from the date of last dose of study drug until disease progression. Tests to be performed are listed in Appendix D. Patients will not be followed up for survival if they start any subsequent therapy.

The following tests will be done during follow up visits:

- Medical history will be updated
- Physical examination, including weight and vital signs (includes blood pressure, heart rate, breathing rate, and oral temperature)
- CBC, including 3-part differential and platelets
- CMP
- 24-hour urine collection for 5-HIAA testing
- CT scan of the chest, a CT scan of the abdomen/pelvis .

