Appendix D: Schedule of Assessments (continued)

- a Baseline procedures including medical history, physical examination, peripheral neuropathy assessment, 12-lead ECG, ECOG PS, CBC, CMP, PT/PTT/INR, and serum or urine pregnancy test should be done \leq 7 days prior to initiation of treatment. However, if these initial examinations are obtained within 72 hours of Cycle 1 Day 1 they do not have to be repeated. Scans should be performed \leq 28 days prior to initiation of treatment, to document measurable or evaluable disease.
- b Physical examination will include measurements of height (pre-treatment visit only), weight, and vital signs.
- c Vital signs will include resting heart rate, blood pressure, respiratory rate, and temperature.
- d ECHO with calculated LVEF (repeat if/when clinically indicated). MUGA is acceptable if ECHO is not available.
- e CMP will include measurements of glucose, BUN, creatinine, sodium, potassium, chloride, calcium, CO², ALP, AST, ALT, total bilirubin, total protein, and albumin.
- f If PT/PTT/INR are normal at baseline they do not need to be repeated. Patients requiring the initiation of an anti-coagulation therapy during study treatment should have coagulation tests performed according to standard practice guidelines.
- g Serum or urine pregnancy tests are to be conducted in women of childbearing potential at the beginning of the study and at the end of study visit or 30 days post last dose..
- h If available, archival tissue samples will be requested by study site personnel.
- i Fasting (overnight) serum chromagranin A test will be done during screening and then on Day 1 of each cycle.
- j 24 hour urine for 5-HIAA will be done during screening and then every 3 cycles to assess response.
- k CT scans of the chest \leq 4 weeks prior to initiation of treatment and then every 3 cycles during the treatment and at the end of study visit, if no PD and not done within prior 6 weeks.
- 1 CT scans of the abdomen/pelvis \leq 4 weeks prior to initiation of treatment and then every 3 cycles during the treatment and at the end of study visit.
- m Patients should visit the study center \leq 30 days for end-of-treatment assessments. Patients must be followed for AEs for 30 calendar days after the last dose of study drug.

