Ultrasound:	When the primary study endpoint is objective response, ultrasound should not be used to measure tumor lesions. It is, however, a possible alternative to clinical measurements of superficial palpable lymph nodes, subcutaneous lesions, and thyroid nodules. Ultrasound may also be useful to confirm the complete disappearance of superficial lesions usually assessed by clinical examination.
Endoscopy and Laparoscopy:	Use of endoscopy and laparoscopy for objective tumor evaluation has not yet been fully and widely validated. Therefore, use of these techniques for objective tumor response should be restricted to validation purposes in specialized centers. Such techniques can be useful in confirming complete pathological response when biopsies are obtained.
Tumor Markers:	Tumor markers alone cannot be used to assess response. If markers are initially above the upper limit of normal, they must normalize for a subject to be considered in complete clinical response when all lesions have disappeared.
Cytology and Histology:	Cytology and histology can be used to differentiate between partial response (PR) and complete response (CR) in rare cases (e.g., after treatment to differentiate between residual benign lesions and residual malignant lesions in tumor types such as germ cell tumors).

CONFIDENTIAL

STUDY DRUG(S): CARFILZOMIB AMENDMENT 2 DATE: 25 FEBRUARY 2015

Response Criteria

Evaluation of Target Lesions

Complete Response (CR):	Disappearance of all target lesions.		
Partial Response (PR):	At least a 30% decrease in the sum of diameters of target lesions, taking as reference the baseline sum diameters		
Stable Disease (SD):	Neither sufficient shrinkage to qualify for PR nor sufficient increase to qualify for PD, taking as reference the smallest (nadir) sum of diameters since the treatment started.		
Progressive Disease (PD):	At least a 20% increase in the sum of the diameters of target lesions, taking as reference the smallest (nadir) sum since the treatment started, or the appearance of one or more new lesions. Requires not only 20% increase, but absolute increase of a minimum of 5 mm over sum.		

Evaluation of Non-Target Lesions

Complete Response (CR):	Disappearance of all non-target lesions and normalization of tumor markers. All lymph nodes must be non-pathological in size (<<10 mm short axis).		
Stable Disease (SD):	Persistence of one or more non-target lesions and/or persistence of tumor marker level above the normal limits.		

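### Section 7.2 accepts a baseline CT without the pelvis, although later scans cover the pelvis and any new lesion is scored as progression

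*Combined protocol and SAP*

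**What the plan says.** **Baseline.** The imaging bullet in Section 7.2 opens with "CT scans of the chest, abdomen and pelvis ≤28 days prior to initiation of study treatment" and then relaxes this: "CT scan of abdomen and pelvis is preferred, but CT scan of abdomen is acceptable". The Appendix D table lists abdomen/pelvis CT at baseline. Its footnote l times that scan at no more than 4 "weeks prior to initiation of treatment and then every 3 cycles during the treatment and at the end of study visit", with no abdomen-only option.

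**On treatment.** Section 5.2 refers restaging every 3 cycles to Appendix D. Section 7.4 lists "CT scans of chest, abdomen and pelvis (if abnormal at baseline", and the parenthesis ends there.

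**After treatment.** Section 7.5 includes the pelvis in the end-of-treatment CT. Section 7.6.1 asks for a "CT scan of the chest, a CT scan of the abdomen/pelvis" in patients who stop before progression. Neither refers to baseline findings.

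**Scoring.** Appendix E counts as progression a sufficient increase in target lesions "or the appearance of one or more new lesions". Its response table returns PD for a new lesion whatever the target and non-target lesions do. It also expects every lesion that is not a target lesion to be listed as non-target at baseline. It does not say how to score a lesion found in a region with no baseline image.

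**The concern.** A new lesion can be called new only if the same region was imaged before treatment. A site that uses the 7.2 allowance has no baseline record of the pelvis and cannot complete the lesion inventory that Appendix E expects. If the pelvis is scanned later, a lesion that was there all along has no baseline entry, and the scoring table makes it progression.

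Three endpoints depend on that call:

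- **PFS** (Section 10.4.1) takes RECIST progression as its event, so a false call shortens it.
- **ORR** is exposed because Appendix E records best response only up to progression. False progression at the first scan removes a patient whose target lesions are shrinking.
- **The disease-control endpoint** (defined as the clinical benefit rate in 10.4.1) needs stable disease for at least 6 cycles, which false progression after 3 cycles rules out.

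The error would depend on local imaging habit rather than on the drug.

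**Working it through.** **1. Which regions are covered, and when**

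| Time | Source | Pelvis scanned? |
|---|---|---|
| Baseline | Section 7.2 | Preferred, not required |
| Baseline | Appendix D, footnote l | Yes |
| Every 3 cycles | Appendix D, footnote l | Yes |
| Every 3 cycles | Section 7.4 | Unclear: conditional on a baseline abnormality |
| End of treatment | Section 7.5 | Yes, not tied to baseline findings |
| Follow-up before progression | Section 7.6.1 | Yes, not tied to baseline findings |

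Section 7.2 and Appendix D disagree at baseline. Section 7.4 and Appendix D disagree on treatment. The 7.4 condition may apply to the pelvis alone or to all three regions, and it has no clear meaning for a region that was never scanned.

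**2. When a false new lesion could appear**

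Under Appendix D the first restaging is at 3 × 28 = 84 days, or 12 weeks. If 7.4 is read as skipping a pelvis not shown to be abnormal, pelvic disease goes unassessed on treatment. The first pelvic scan is then the one in 7.5 or 7.6.1. In that case a response already confirmed on treatment stands, and the error falls mainly on PFS.

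**3. The plan's own design figures**

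Inputs from Section 10.2: null rate 0.05, alternative 0.15, stop at 1 or fewer responses in 23, reject at 6 or more in 56, so 33 patients in stage 2. With X2 the stage 2 responses,

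P(reject | p) = Σ over x = 2 to 23 of C(23, x) p^x (1 − p)^(23 − x) × P(X2 ≥ 6 − x; 33, p).

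This gives 0.04996 at p = 0.05 and 0.8003 at p = 0.15. The stated type I error of 0.05 and power of 80% reproduce.

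**4. Sensitivity of power**

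The documents do not give the share affected. Let q be the assumed share of true responders lost to false progression. The observed rate is then p = 0.15 × (1 − q), put into the same formula. The stop probability is P(X1 ≤ 1; 23, p), with X1 the stage 1 responses.

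| q | 0.15 × (1 − q) | Power | Chance of stopping after 23 |
|---|---|---|---|
| 0 | 0.1500 | 0.800 | 0.120 |
| 1% | 0.1485 | 0.793 | 0.124 |
| 2% | 0.1470 | 0.785 | 0.128 |
| 5% | 0.1425 | 0.761 | 0.141 |
| 10% | 0.1350 | 0.715 | 0.163 |

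What q requires: if unseen pelvic disease is unrelated to response and every affected patient is scanned later, q = s × v. Here s is the share with an abdomen-only baseline scan and v the share of those with an unseen pelvic lesion. Examples, all assumed: 0.10 × 0.10 = 1%; 0.20 × 0.10 = 2%; 0.25 × 0.20 = 5%; 0.50 × 0.20 = 10%.

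In expected responders among 56, 56 × 0.15 = 8.4 falls by 8.4 × 0.02 = 0.17 at q = 2%, and by 8.4 × 0.10 = 0.84 at q = 10%.

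**5. PFS**

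Here every affected patient counts, not only responders. If the same shares applied to all 62 enrolled, 62 × 0.02 = 1.2 to 62 × 0.10 = 6.2 patients would get an event too early, at about 12 weeks if Appendix D is followed.

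**The case against.** **The 7.4 condition may prevent the problem on treatment.** A reader might infer that the rules force a false progression at week 12 in every such patient. They do not: on one natural reading of 7.4, a pelvis with no known baseline abnormality is not rescanned. This stands as a limit on timing. It does not remove the problem, because Section 5.2 sends restaging to Appendix D, which is unconditional, and Sections 7.5 and 7.6.1 scan the pelvis anyway.

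**The pelvis is already the default.** Section 7.2 opens with it, and Section 7.1 calls Appendix D the complete schedule. That narrows exposure to sites that use the allowance, but a site doing so complies with 7.2.

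**Slow growth does not show that such lesions predate treatment.** Section 1.1 says "These tumors are generally slow-growing and can be present throughout the GI tract", and a reader might infer that a pelvic lesion seen at 12 weeks was probably present at baseline. That sentence describes GI carcinoids and where they can be present in the GI tract. The trial also enrols pancreatic islet cell and other neuroendocrine carcinomas. It makes a pre-existing lesion plausible, but gives no frequency.

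**Progression does not always end treatment.** Section 7.4 says patients with progression should be discontinued. Section 3.3 allows continuation for clinical benefit after consultation with the Medical Monitor, and Section 5.1.1 speaks of confirmed progression. Loss of treatment is therefore possible but not automatic.

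**An exception in Appendix E has its own cost.** Exempting lesions in unscanned regions would change the scoring of the primary endpoint during an open-label, single-arm study. It could also delay true progression when the lesion really is new. This objection stands, so the remedy leaves the primary scoring alone.

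**Conclusion.** The point holds as an internal inconsistency with a one-sided consequence. Sections 7.2, 7.4 and Appendix D do not agree on pelvic coverage, and Appendix E scores any new lesion as progression without asking whether the region had been imaged before. Where the 7.2 allowance is used, the pelvis holds unseen disease and a later scan covers it, false progression can be recorded. The bias is downward for PFS, and possibly for ORR and disease control.

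Its size cannot be derived from the documents. The power figures rest on an assumed q, independence of response, and false progression before a response is confirmed. Power is 0.793 at q = 1% and 0.785 at 2%, which is a small loss, and 0.761 at 5% and 0.715 at 10%. A reader might infer from the last two that the trial is materially underpowered. The documents do not support that, because nothing in them places q at 5% or more. The case for correction rests on its low cost and on the fact that a missing baseline scan cannot be recovered later.

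**What to change.** 1. In Section 7.2 delete "CT scan of abdomen and pelvis is preferred, but CT scan of abdomen is acceptable", so that baseline imaging matches Appendix D.
2. Reconcile the condition in Section 7.4 with Appendix D, so that baseline and on-treatment scans cover the same regions.
3. For patients already enrolled with an abdomen-only baseline scan, keep the RECIST scoring for the primary analysis. Flag any progression that rests only on a lesion in a region not imaged at baseline, and report a sensitivity analysis of ORR and PFS for those flagged cases.

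Cost: two short text edits and one small sensitivity analysis. Sites now using abdomen-only CT would extend the same scan to the pelvis. Nothing is added to the Appendix D schedule, and the sample size is unchanged.

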7.3 Study Treatment Assessments

7.3.1 Days 1, 8, and 15 of each cycle

- Physical examination including measurement of weight, (Day 1 only)
- Vital signs
- ECOG performance status
- Adverse event (AE) assessment
- Concomitant medication review
- CBC, including 3-part differential and platelets (may be done up to 72 hours prior to treatment)
- CMP (may be done up to 72 hours prior to treatment)
- Fasting serum chromogranin A (Day 1 only)
- 24-hour urine for 5-HIAA (Day 1 only)

CONFIDENTIAL

STUDY DRUG(S): CARFILZOMIB AMENDMENT 2 DATE: 25 FEBRUARY 2015

7.3.2 Days 2, 9, and 16 of each cycle

- Vital signs
- AE assessment
- Concomitant medication review

7.4 Response Assessment Every 3 Cycles

Patients will be evaluated for response to treatment after every 3 cycles of treatment. The following assessments will be performed:

- CT scans of chest, abdomen and pelvis (if abnormal at baseline)
- 24 hour urine for 5-HIAA

Patients with progressive disease or unacceptable toxicity should be discontinued from the study; patients with stable disease or response to therapy will continue treatment.

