3. STUDY PATIENT POPULATION AND DISCONTINUATION

3.1 Inclusion Criteria

Patients must meet the following criteria in order to be included in the research study:

1. Patients with biopsy-proven advanced, unresectable or metastatic, well-to-moderately differentiated (or low-grade) neuroendocrine carcinoma, including typical carcinoid, *CONFIDENTIAL*

STUDY DRUG(S): CARFILZOMIB AMENDMENT 2 DATE: 25 FEBRUARY 2015

pancreatic islet cell and other well- to-moderately differentiated neuroendocrine carcinomas.

- 2. Patients must have at least one unidimensional measurable lesion definable by magnetic resonance imaging (MRI) or computed tomography (CT) scan. Disease must be measurable per Response Evaluation Criteria in Solid Tumors (RECIST) v 1.1 criteria (Appendix E).
- 3. Patients currently receiving or previously treated with single agent somatostatin analogues (e.g. sandostatin LAR[®] or lanreotide) are eligible. However, this is not a mandatory criterion to be included in the study.
- 4. Eastern Cooperative Oncology Group (ECOG) Performance Status score of ECOG PS 0 or 1 (Appendix A).
- 5. Adequate hematologic function defined as:
 - Absolute neutrophil count (ANC) $\geq 1500/\mu L$
 - Hemoglobin (Hgb) $\geq 9 \text{ g/dL}$
 - Platelets $\geq 100,000/\mu L$
- 6. Adequate liver function defined as:
 - Alanine aminotransferase (ALT) ≤ 2.5 x upper limit of normal (ULN) or <5.0 x ULN in patients with liver metastases
 - Aspartate aminotransferase (AST) \leq 2.5 x ULN or \leq 5.0 x ULN in patients with liver metastases
 - Total bilirubin ≤1.5 x ULN (unless the patient has Grade 1 bilirubin elevation due to Gilbert's disease or a similar syndrome involving slow conjugation of bilirubin)
- 7. Adequate renal function defined as serum creatinine ≤2.0mg/dL or calculated creatinine clearance ≥30 mL/min as calculated by Cockcroft and Gault Formula.
- 8. Women of childbearing potential (WoCBP) must have a negative serum or urine pregnancy test. Serum pregnancy test should be performed ≤7 days or urine pregnancy test should be performed within ≤3 days prior to start of treatment. Another pregnancy test will be performed within 30 days following last dose of study drug. WoCBP or men with partners of childbearing potential must use effective birth control measures during treatment (Appendix C). If a woman becomes pregnant or suspects she is pregnant while participating in this study, she must agree to inform her treating physician immediately.

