5.2 Treatment Duration

Patients will be evaluated for toxicity at the start of each cycle. Every 3 cycles, restaging will occur with imaging, laboratory chemistries, and tumor markers as defined in Appendix D. Patients will continue on treatment until progression as defined in Appendix E or intolerance to side effects.

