Progressive Disease (PD):	Appearance of one or more new lesions and/or unequivocal progression of existing non-target lesions. When the subject also has measurable disease, to achieve "unequivocal progression" on the basis of the non-target disease, there must be an overall level of substantial worsening in non-target disease such that, even in presence of SD or PR in the target disease, the overall tumor burden has increased sufficiently to merit discontinuation of therapy.		

Evaluation of Best Overall Response

The best overall response is the best response recorded from the start of the treatment until disease progression/recurrence (taking as reference for PD the smallest measurements recorded since the treatment started). In general, the subject's best response assignment will depend on the achievement of both measurement and confirmation criteria.

Confirmation of response (by repeat scans after 4 weeks or as specified in the protocol) is required for studies in which response rate is the primary endpoint, but is not required in randomized studies or studies with primary survival endpoints (i.e., where response is not a primary endpoint).

CONFIDENTIAL

Target Lesions	Non-Target Lesions	New Lesions	Overall Response	
CR	CR	NO	CR	
CR	SD	NO	PR	
CR	NE	NO	PR	
PR	SD OR NE	NO	PR	
SD	SD OR NE	NO	SD	
PD	ANY	YES OR NO	PD	
ANY	PD	YES OR NO	PD	
ANY	ANY	YES	PD	

In some circumstances, it may be difficult to distinguish residual disease from normal tissue. When the evaluation of a CR depends upon this determination, it is recommended that the residual lesion be investigated by fine needle aspirate or biopsy to confirm the CR status.

When nodal disease is included in the sum of target lesions, and the nodes decrease to "normal" size (<<10 mm), they may still have a measurement reported on scans. This measurement should be recorded even though the nodes are normal in order not to overstate progression, should it be based on increase in size of the nodes. As noted earlier, this means that subjects with CR may not have a total sum of "zero" on the eCRF.

CONFIDENTIAL

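### Section 7.4 makes the every-3-cycle CT conditional on an abnormal baseline while Appendix D does not; under two of three readings, a region clear at baseline is not rescanned on treatment, which can lengthen PFS and raise CBR

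*Combined protocol and SAP*

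**What the plan says.** Section 7.4, which covers the response assessment every 3 cycles, lists "CT scans of chest, abdomen and pelvis (if abnormal at baseline". The parenthesis ends there.

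Appendix D sets no baseline condition. Footnote k requires chest CT at baseline, "then every 3 cycles during the treatment and at the end of study visit, if no PD and not done within prior 6 weeks". The closing condition concerns the end-of-study scan and does not refer to baseline findings. Footnote l requires abdomen/pelvis CT within 4 "weeks prior to initiation of treatment and then every 3 cycles during the treatment and at the end of study visit".

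Two sections direct the reader to Appendix D. Section 5.2 says: "Every 3 cycles, restaging will occur with imaging, laboratory chemistries, and tumor markers as defined in Appendix D". Section 7.1 says: "The complete Schedule of Assessments for this study is shown in Appendix D". Neither states that Appendix D overrides Section 7.4 where they differ.

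Two other provisions matter. Eligibility (3.1, criterion 2) states: "Patients must have at least one unidimensional measurable lesion definable by magnetic resonance imaging (MRI) or computed tomography (CT) scan". In Appendix E, progression on target lesions includes "or the appearance of one or more new lesions", and progression on non-target lesions includes "Appearance of one or more new lesions and/or unequivocal progression of existing non-target lesions". A new lesion is therefore progression wherever it appears, and under 10.4.1 progression is a PFS event.

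**The concern.** Whether a region was abnormal at baseline never changes. If the qualifier applies by region, a region clear at baseline is left out of every on-treatment restaging, not just one. Appendix E counts a new lesion as progression, but a lesion in an unscanned region will not be seen on schedule.

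Two endpoints are exposed. PFS depends on the date progression is recorded, and 10.4.1 censors patients without recorded progression at the last tumor assessment. CBR counts stable disease lasting at least 6 cycles, so a patient could qualify although one region had not been imaged since baseline. A site following 7.4 and a site following Appendix D could each claim compliance while ascertaining progression differently.

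**Working it through.** The plan gives no figure for this point, so there is none to reproduce. The check compares the passages and counts scheduled scans.

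**Inputs.** Cycle length is 28 days (Section 5). Restaging is every 3 cycles (5.2, 7.4). The CBR threshold for stable disease is 6 cycles (10.4.1). PFS is evaluated 6 and 12 months after the last patient is enrolled (10.1, Appendix D footnote n).

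**Scan count.**
- Restaging interval: 3 × 28 = 84 days.
- Stable-disease threshold: 6 × 28 = 168 days.
- Restagings up to the threshold: 168 / 84 = 2, at about days 84 and 168.

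**Three readings of the parenthesis.**

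| The qualifier applies to | Region affected | Scans of it by day 168 under 7.4 | Under Appendix D |
|---|---|---|---|
| each region separately | any region clear at baseline | 0 of 2 | 2 of 2 |
| the pelvis only | the pelvis, if clear at baseline | 0 of 2 | 2 of 2 |
| the baseline CT as a whole | none, since eligibility requires measurable disease | 2 of 2 | 2 of 2 |

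**A new lesion confined to an affected region, under the first two readings.**

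1. *The patient stops treatment with no progression recorded.* Section 7.5 calls for CT if there is no progression or no scan in the prior 6 weeks, so the absence of progression is enough. Footnote k needs both conditions; a chest skipped on treatment meets the second unless the patient stops very soon after the baseline scan. Footnote l has no condition. All three wordings would normally image the region at end of treatment, so progression is recorded late.
2. *Progression is found elsewhere first.* An event is recorded then, so the delay ends at that date.
3. *The patient is still on treatment at the 6- or 12-month PFS evaluation.* No scan of the region has been scheduled, so the progression is missing. The patient is censored at an assessment that did not include the region.

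In the first and second cases PFS can be too long. In the third an event becomes a censored observation. A patient scored stable at the cycle-6 restaging can count towards CBR in any of the three.

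**Two related conflicts.**
- The two end-of-treatment CT conditions are joined by *or* in 7.5 and by *and* in footnote k; footnote l has none.
- Section 7.2 accepts a baseline CT of the abdomen alone. A pelvis not imaged at baseline cannot be shown to have been abnormal, so the first two readings of 7.4 would not schedule it. Footnote l would scan it without a comparator, and a pre-existing lesion could be taken for a new one. No net direction is claimed for either conflict.

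**Size.** A shift in PFS or CBR would depend on the share of first progressions confined to a region clear at baseline and on how many sites follow 7.4. The documents give neither.

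**The case against.** The strongest reply is that the conflict is harmless. If the parenthesis refers to the baseline CT as a whole, essentially every eligible patient meets it and 7.4 agrees with Appendix D. The pelvis-only reading is also natural, because 7.2 makes only the pelvis optional. Sections 5.2, 7.1, 7.5 and 7.6.1 all refer to Appendix D and none refers to 7.4, so sites may well follow the unconditional schedule. PFS and CBR are reported descriptively, without a test or comparator.

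Much of this stands. The region-by-region reading is only one of three and should not be called the literal one, and differing practice between sites is a possibility, not a finding. But no precedence rule exists, and 7.4 is the section devoted to response assessment.

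Stronger conclusions are tempting, but the documents do not support them:

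- *That 7.4 could remove all restaging CT.* Every patient must have measurable disease, so it cannot.
- *That progression would usually go unrecorded because follow-up stops when another therapy starts (footnote n).* The end-of-treatment CT would normally image a skipped region before that happens.
- *That the 3-cycle minimum in 10.5.1 fixes when progression goes missing.* The stated PFS time points are 6 and 12 months after last enrolment.
- *That the go/no-go decision on ORR is affected.* That would need confirmed shrinkage of target lesions together with a new lesion only in an unscanned region. The documents give no basis for saying how often, if ever, this occurs.

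**Conclusion.** The inconsistency is real and should be corrected. Under the each-region or pelvis-only reading, a region clear at baseline has no scheduled on-treatment CT: 0 of 2 restaging scans by about day 168, against 2 of 2 under Appendix D. Progression there would normally be recorded only at the end-of-treatment CT or when progression is found elsewhere, or would be missing at a PFS evaluation for a patient still on treatment. The possible effect is longer PFS and higher CBR. Under the pelvis-only reading it is limited to the pelvis; under the whole-CT reading there is none.

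The conclusion assumes that some sites follow 7.4 under one of the first two readings, and that some progressions first appear in a region clear at baseline. The documents settle neither, so no size is given. Confidence is high in the textual mismatch and the possible direction, not in any amount.

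**What to change.** Delete the parenthesis in 7.4 so that it matches Appendix D footnotes k and l. In the same edit, state one end-of-treatment CT condition in 7.5 and footnotes k and l, and reconcile the abdomen-only baseline allowed in 7.2 with the abdomen/pelvis CT in footnote l.

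Report the number of patients already restaged with an Appendix D region unscanned. That count is enough: with at most 62 patients across multiple sites, a sensitivity analysis by site practice would rest on very small, confounded groups. The PFS censoring rule in 10.4.1 need not change for this point.

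The cost is wording only where sites already follow Appendix D. Sites that followed 7.4 would do some additional CT, but none beyond what Appendix D already schedules.
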